The overall Specific Aim of this proposal is to determine the effect of opioid taper on pain sensitivity in patients with chronic pain. Specifically, in a well-characterized sample of men and women with chronic neuropathic pain and receiving high-dose opioid therapy (200mg morphine equivalents/day [MED]), experimental pain responses will be serially described over the course of an individualized opioid taper to a safer dose of 90mg MED for up to 12 months. Changes will be inspected within-subject over time, and pain perception will be measured with two valid and reliable experimental pain induction techniques commonly used to measure OIH (cold-pressor, quantitative sensory testing); in addition, related functional improvements and subject-level predictors of response will be described. Hypothesis 1. Subjects undergoing opioid taper will have improved pain responses over time compared to within-subject baseline as measured by cold-pressor and quantitative sensory pain testing. Hypothesis 2. Improvements in experimental pain responses will be positively related to improved functional outcomes compared to within-subject baseline as measured by the PROMIS physical, mental and social health measures. Hypothesis 3. Degree of improvement in experimental pain responses related to opioid taper will be predicted by demographic, pain, and opioid use history characteristics of the subject. Data showing that pain perception improves as opioids are withdrawn would provide an evidence-based, mechanistic rationale for opioid taper in patients with chronic pain and have the potential to support a sea-change in opioid prescription practices. In that ongoing opioid therapy brings with it significant health risks for the patient and the community, it is critical that empirical evidence of its efficacy be demonstrated to balance the benefits with the risks of adverse events, potential misuse and abuse, and patient safety.

Primary outcome variable(s)

The primary dependent variable, pain perception, will be measured using two highly reliable and valid pain induction techniques, the cold-pressor test (CPT) and quantitative sensory testing (QST), employing procedures consistent with those described in the literature. Order of pain testing will vary, and three aspects of the pain response will be captured at each study session: evoked pain; temporal summation; and conditioned pain modulation, which map on to the hypothesized peripheral, spinal and supra-spinal mechanisms of OIH.

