
Study Design

Phase*

Not applicable

Design

A prospective time-series survey design will be utilized to measure the experimental (CPT and QST) pain responses of chronic pain patients on high-dose opioid therapy (200mg MED) prior to and then regularly during and following a voluntary opioid taper. Data will be collected weekly during the active taper period; once the subject has reached a stable maintenance dose (90 MED), assessments will occur monthly until month 12. Because our previous work has shown stability in pain responses in patients on

high-dose opioid therapy over time (6 months), and the clinical imperative of tapering patients to safer doses, a control group of patients maintained on high-dose therapy is not included. Consistent with expert opinion in the field, a longitudinal within-subject design is planned.

Study duration

The overall duration of the study is two years, during which time all subjects will be enrolled and complete the study. Data will be collected weekly during the active taper period; once the subject has reached a stable maintenance dose (less than or equal to 90 MED), assessments will occur monthly until month 12. If funded, the study would begin Oct 1, 2018.

Resources necessary for human research protection

Describe research staff and justify that the staff are adequate in number and qualifications to conduct the research. Describe how you will ensure that all staff assisting with the research are adequately informed about the protocol and their research related duties. Please allow adequate time for the researchers to conduct and complete the research. Please confirm that there are adequate facilities for the research.

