Standard of Care: In light of the demonstrated health risks associated with daily opioid doses greater than 90mg MED, current practice at the Penn Pain Medicine Center is to taper all chronic pain patients down to or below this MED and to stabilize on the lowest effective dose as agreed upon by the patient and prescriber. The actual rate of taper varies with tolerability and availability of dosages of opioid, but averages 10-15% decrease/month. Final stabilization dose also varies between patients but the goal to achieve a daily dose of 90mg MED. Prior to attempting taper, an adequate trial of all non-opioid and non-pharmacologic interventions are provided so that the patients chronic pain is under maximal control. Research Purposes: Baseline Study Session: Study data collection will begin immediately following consent, with the collection of urine toxicology, chronic pain and opioid use history, and baseline pain testing (see attached Data Collection Schedule). It is expected that it will take 30min to complete the baseline measures and another 30min to perform the pain testing battery, totaling 60min for the first session; subsequent sessions should last no longer than 30min. Study Sessions. All data collection will take place in a private office located in the Penn Pain Medicine Center, with sessions scheduled within 3hrs of morning opioid dose, and subjects instructed to ingest no caffeine or nicotine for 1hr prior to each session. Concurrent medication use since last visit, and last menstrual period date for female participants will be documented. A withdrawal score and urine sample for toxicology will be collected immediately prior to pain testing to verify compliance with opioid treatment. Sessions will be scheduled to coincide with regular clinic visits as possible. All study data will be collected using REDCap (Research Electronic Data Capture), utilizing PhenX data collection tools as available. Pain Responses: The primary dependent variable, pain, will be measured using two highly reliable and valid pain induction techniques, the CPT and QST, employing procedures consistent with those described in the literature. Order of pain testing will vary, and three aspects of the pain response will be captured at each study session: evoked pain; temporal summation; and conditioned pain modulation, which map on to the hypothesized peripheral, spinal and supra-spinal mechanisms of OIH. Protocols for each assay have been uploaded. Evoked pain perception: The CPT apparatus consists of a circulating water bath maintained at $1^{\circ}\text{C} \pm 0.5^{\circ}\text{C}$, into which subjects immerse their dominant hand and forearm to elicit a nociceptive response. Elapsed time until pain threshold and tolerance are reached measures evoked pain. A stopwatch is simultaneously activated with arm immersion, and subjects instructed to indicate when the cold sensation becomes a painful sensation (pain threshold), and when the pain becomes subjectively intolerable or spontaneous hand removal (pain tolerance). Immediately after hand withdrawal, subjects are asked to mark maximal pain intensity on a computerized visual analogue scale (Co-VAS, 0-100). Temporal Summation (TS): As a component of QST, a thermal testing analyzer (TSA; Medoc TSA-2001 device) with a sized 30 x 30 mm Peltier thermode, is used for the assessment

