as a biological variable will be considered in all analyses. Statistical Analyses. The effect of opioid taper on changes in pain responses (CPT, QST), and functional outcomes (PROMIS domains) over time will be examined using longitudinal mixed-effects regression modeling, using general linear regression modeling with regularization as a function of baseline dose, end dose, and taper rate. These longitudinal profiles will be examined using a linear mixed effects framework with SAS Proc Mixed in which all available data collected during follow-up are used. Mixed models can account for the correlation between repeated measures and handle non-excessive missing data better than traditional models and allow for use of time-independent and time-dependent covariates. To assess patterns of attrition over time, a comparison of withdrawal rates and time to withdrawal will be included. Separate mixed effects regression models will be generated for each of the continuous outcome measures of interest (pain responses, functional outcomes). Random slopes and intercepts will be modeled to represent the participant-level deviation from the fixed-effect slope over time and intercept, respectively. Restricted maximum likelihood estimation will be used and the most appropriate covariance structure examined. Scores will be analyzed as repeated observations of the dependent variable, with mean-centered baseline outcome scores serving as a covariate. Other predictor variables will include baseline demographic characteristics of the patient, severity and chronicity of pain suffered, and opioid use history. Baseline measures will be analyzed as time-independent covariates. The Akaike information criterion will be used to evaluate overall model fit and to select the best-fitting longitudinal change pattern. .

The following documents are currently attached to this item:

There are no documents attached for this item.

Data confidentiality

- x Paper-based records will be kept in a secure location and only be accessible to personnel involved in the study.**
- x Computer-based files will only be made available to personnel involved in the study through the use of access privileges and passwords.**
- x Prior to access to any study-related information, personnel will be required to sign statements agreeing to protect the security and confidentiality of identifiable information.**
- x Wherever feasible, identifiers will be removed from study-related information.**

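### End dose and taper rate enter the outcome models as predictors, but both arise after baseline and can follow the patient's clinical course, so their coefficients could reflect confounding or reverse causation

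*Combined protocol and SAP*

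**What the plan says.** The Statistical Analyses part of the Analysis Plan sets out to examine the effect of taper on pain responses and PROMIS domains over time, "using general linear regression modeling with regularization as a function of baseline dose, end dose, and taper rate". It does not say whether taper rate means the planned or the actual rate, and it does not call these terms associational.

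The Standard of Care text under Procedures explains how the two quantities come about. On rate: "The actual rate of taper varies with tolerability and availability of dosages of opioid, but averages 10-15% decrease/month". On final dose, the clinic aims to bring patients to or below the target and "stabilize on the lowest effective dose as agreed upon by the patient and prescriber". It adds: "Final stabilization dose also varies between patients but the goal to achieve a daily dose of 90mg MED".

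No stated hypothesis concerns end dose or taper rate. Hypothesis 1 is change from each subject's own baseline. Hypothesis 3 says that how much the experimental pain measures improve "will be predicted by demographic, pain, and opioid use history characteristics of the subject", and Procedures lists those predictors as collected at baseline. The design is a single group: "a control group of patients maintained on high-dose therapy is not included".

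**The concern.** A regression on end dose and taper rate treats them as exposures that stand apart from the outcome. The protocol's own account suggests otherwise. A patient who is doing badly may be tapered more slowly and settle higher, and one who is doing well may go faster and lower. An association between dose path and pain would then appear even if dose had no effect on pain sensitivity.

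The Background says that knowledge of predictors will support guidance on which patients may benefit from taper. An end-dose or rate coefficient printed beside those predictors could be read as a dose-response effect. Adjusting for a post-baseline variable can also distort the coefficients of the baseline predictors that Hypothesis 3 is about.

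**Working it through.** **1. Plan figure.** The plan gives no figure for these two terms. Its power statements under Accrual concern change in outcome, so there is nothing to reproduce here.

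**2. The three dose terms side by side.**

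| Term | When known | What sets it | Named in a hypothesis |
|---|---|---|---|
| Baseline dose | Baseline | Prior treatment | Yes, as opioid use history (Hypothesis 3) |
| Taper rate | During taper, if actual; not defined | Tolerability, available dosages | No |
| End dose | End of taper | Effectiveness, agreed with patient | No |

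**3. Timing.** Assume a fall from 200 to 90 mg MED at the stated average of 10-15% per month.
- Compounding: ln(90/200)/ln(0.90) = 7.6 months; ln(90/200)/ln(0.85) = 4.9 months.
- Fixed steps of baseline dose: 110/20 = 5.5 months; 110/30 = 3.7 months.

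With weekly testing (52/12 = 4.33 weeks per month), roughly 16 to 33 sessions come before the end dose is known. That later quantity would be used to explain the earlier scores.

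**4. Illustration with one predictor.** Assume no causal effect of dose, and a correlation r between the taper variable and the subject's pain trend that arises only from clinical course. The false-positive rate is then the power of a correlation test, approximately Φ(√(n−3)·atanh(r) − z), with z = 1.960 at alpha 0.05 and 2.498 at 0.05/4 = 0.0125 (two-sided). For n = 25 and r = 0.3: √22 × 0.3095 = 1.452. Then Φ(1.452 − 1.960) = 31% and Φ(1.452 − 2.498) = 15%. Simulated values:

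| n | alpha | r = 0.2 | 0.3 | 0.4 | 0.5 |
|---|---|---|---|---|---|
| 25 | 0.05 | 16% | 31% | 52% | 75% |
| 25 | 0.0125 | 6% | 15% | 31% | 54% |
| 20 | 0.05 | 13% | 25% | 43% | 64% |

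At r = 0 the rate is the nominal one. The n = 20 row assumes that the 25% oversampling leaves 25/1.25 = 20 subjects.

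**5. All three terms together.** A second simulation fitted ordinary least squares on baseline dose, end dose and rate, with dose path driven by a tolerability variable (tolerability-dose correlation 0.5 to 0.8) and no true dose effect. At n = 25 and alpha 0.05, the joint test of end dose and rate rejects in about 5% of samples when pain and tolerability are uncorrelated. It rejects in 12-17% at a correlation of 0.3 and 24-48% at 0.5. The end-dose term alone rejects less often, about 8% and 15%, because the two terms share the signal.

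**6. Effect on baseline predictors.** Take a baseline predictor with no effect on response but correlation 0.5 with end dose, where end dose correlates r with response. In standard-deviation units its adjusted coefficient is −0.5r/(1 − 0.5²). That is −0.15/0.75 = −0.20 at r = 0.3 and −0.25/0.75 = −0.33 at r = 0.5. At n = 25 and alpha 0.05, simulation finds it falsely significant in about 13% and 36-37% of samples.

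None of these simulations includes the repeated measures, random slopes or regularization of the plan. Regularization shrinks coefficients but does not remove this kind of bias.

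**The case against.** Several replies have force.

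- **The rate may be a planned one.** The plan says only taper rate, and elsewhere the taper is described as prescribed and individualized. For rate, the secure defect is that it is undefined; the case on end dose is firmer.
- **The modelled pain measures need not drive dosing.** A reader might infer that end dose and rate are consequences of the cold-pressor and sensory-testing results. The documents do not support that: nothing says prescribers see or act on those results, and dosage availability is unrelated to pain trend. For these assays the issue is confounding by clinical course, and only so far as they track clinical pain. Hypothesis 2 expects them to track function, which makes a link plausible, but no value is given. Reverse causation is more direct for PROMIS pain intensity and interference.
- **The main result can stand.** Hypothesis 1 is within-subject change, and the study is described as an observational pilot.
- **Direction is not fixed.** Withdrawal discomfort could make faster tapering look worse rather than better.
- **Safeguards are feasible.** The mixed-model framework allows time-dependent covariates, and withdrawal scores are collected. The plan mentions the former only as a general advantage and names neither dose over time nor withdrawal score as a covariate.

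These points limit the strength of the claim. They do not supply a reason to have two post-baseline, patient-responsive variables in the main models without a caveat.

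**Conclusion.** The point holds in this form: the end-dose and taper-rate coefficients could arise from confounding by clinical course, or from reverse causation for the PROMIS pain scores. Adjusting for them can also bias the baseline-predictor coefficients. A reader might go further and infer that the model would show a dose-response when none exists, or that the primary analysis is invalid. Neither follows. At r = 0.2 or 0.3 a spurious result is less likely than not, and the Hypothesis 1 time slope is unaffected when fitted without these terms.

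The size rests on an assumed r and a simplified test. At n = 25 the illustrative false-positive rate runs from 16% to 75% at alpha 0.05, and from 6% to 54% at 0.05/4, as r goes from 0.2 to 0.5. Confidence is higher for end dose than for rate. This should be changed, since the remedy is cheap and no stated hypothesis depends on the terms.

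**What to change.** In the Analysis Plan:

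1. Estimate the Hypothesis 1 time effect and the Hypothesis 3 predictor effects without end dose or actual taper rate. Keep baseline dose and the baseline predictors.
2. Define taper rate. If a taper-speed predictor is wanted, use the planned rate recorded at baseline, before any response is seen.
3. Report actual rate and end dose in a separate analysis labelled associational. As an exploratory alternative, the weekly data would allow a model of lagged time-varying dose against later pain response, adjusted for prior pain response and withdrawal score.

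The cost is analysis-plan wording and, if the planned rate is used, recording the planned schedule at baseline. The downside is that the main models no longer give a dose-response term. No change to any patient's taper is proposed.

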The study will be staff by a 55% FTE Project Director assisted by two part time graduate student research assistants (10hr/week) who will assist with pain testing and data collection. The project director is well-trained and experienced in all study procedures and human subjects research; with the PI, he will ensure the research assistants are trained and qualified to conduct research. Weekly research meetings between the investigators and study staff will occur to ensure staff are adequately informed about the protocol and their research-related duties. The PI has her own locking office space ([name], approximately 170 square feet). All faculty offices come equipped with locked filing cabinets, bookshelves, desk, minimum 4 GHz computer with HP printer, Windows XP service pack 3 operating system, Microsoft Office Professional (Word, Excel, PowerPoint, Access), SPSS or SAS statistical analysis software, and e-mail and internet access. With the same resources, an adjacent cubicle space is dedicated to the study research assistant. NHS copier, printer, fax and scanner facilities are available on each floor. Research visits will take place in a private office at the U Penn Pain Medicine clinic. The Penn Pain Medicine Center currently has eight clinical exam rooms, 7 administrative offices (office manager, physician, fellow, and resident offices), 5 support staff offices (2 billing/new patient coordinator, surgical coordinator, and research coordinator offices). There is a large clinical research area which houses the office of the clinical research coordinator along with 3 bays/exam locations for research patients. Study sessions will occur one of several small (10 ft x 15 ft) private examination rooms located onsite, complete with examining table, chair, bedside stand, desk, computer, and sink.

Characteristics of the Study Population

Target population

The sample will consist of 25 male and female adults with chronic neuropathic pain on opioid therapy and preparing to voluntarily undergo a prescribed opioid taper.

Subjects enrolled by Penn Researchers

25

Subjects enrolled by Collaborating Researchers

0

Accrual

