Participants will be recruited from those treated at the large and nationally-renowned Penn Pain Medicine Center at the University of Pennsylvania Penn Medicine Neuroscience Center. The Penn Pain Medicine Center provides interdisciplinary, multimodal pain care to over 12,000 outpatients annually, an estimated 20% of whom are taking opioids on a regular basis. At any one point in time an estimated 50 patients are undergoing opioid taper, up to half of whom are tapered from opioid doses greater or equal to 200mg MED. Due to anticipated rates of dropout, 25% oversampling for these individuals is planned. Results from previous studies have demonstrated moderate to large effect size estimates of opioids on cold-pressor and QST experimental pain responses. Based on these estimates, a sample size

of 25 will have over 99% power to detect differences in outcome. Using an alpha of 0.05/4 (Bonferroni correction) to account for multiple outcomes, we will have over 90% power to detect significant changes at the 0.01 level for all of the outcomes. Cross-sectional and prospective studies demonstrate statistically significant differences in experimental pain responses with changes between 80-90mg MED (10,11,70); since MED decreases in the proposed work will be 110 MED (tapers from 200MED to 90MED), we anticipate having no difficulty discerning taper effects on pain responses.

Key inclusion criteria

(1) between ages of 21-60; (2) documented chronic neuropathic non-malignant pain condition of at least one year duration; (3) on 200mg MED for at least 6 months; (4) have fully engaged in all prescribed non-opioid pain management treatments; (5) willing to undergo prescribed opioid taper; (6) otherwise in good physical and mental health, or in the care of a physician who is willing to take responsibility for such treatment; and (7) able to understand the purpose and instructions of the study, and provide informed consent as approved by the University of Pennsylvania IRB.

Key exclusion criteria

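### The plan expects dropout from a single-arm voluntary taper, but nothing in it tests whether loss that depends on unseen pain response could produce the improvement claimed under Hypothesis 1.

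*Combined protocol and SAP*

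**What the plan says.** - **Cohort.** Target population: "The sample will consist of 25 male and female adults with chronic neuropathic pain on opioid therapy". Under Design, "a control group of patients maintained on high-dose therapy is not included". Hypothesis 1 (Overall objectives) is improvement over time against each subject's own baseline.
- **Freedom to leave.** Design calls the taper voluntary, and the Consent section lets subjects withdraw at any time.
- **Expected loss.** Accrual: "Due to anticipated rates of dropout, 25% oversampling for these individuals is planned". No dropout rate is given.
- **Model.** The Analysis Plan fits a REML mixed model with random intercepts and slopes to all available follow-up data. Its only missing-data argument is that such models "handle non-excessive missing data better than traditional models". It names no mechanism and no threshold.
- **Attrition.** "To assess patterns of attrition over time, a comparison of withdrawal rates and time to withdrawal will be included". The plan does not say what is compared with what.
- **Follow-up.** Design and Study duration set weekly visits during active taper, then monthly visits to month 12 once the maintenance dose is reached. They give no schedule for a subject whose taper stops before that point.
- **References.** The list includes papers on imputation under truncated follow-up and on non-random missingness. The Analysis Plan applies neither.

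**The concern.** With no second arm, similar dropout elsewhere cannot offset selective loss. If subjects whose pain response is worsening tend to leave, those who remain look better, which is the direction of Hypothesis 1. This is plausible on the documents alone: withdrawal symptoms are scored at every session, and the reference list includes a study whose title reports reduced cold-pain tolerance after opioid detoxification.

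A likelihood-based mixed model is valid if loss depends only on data already recorded (missing at random). The plan relies on that condition without stating it. Recorded data cannot confirm the condition, so the usual safeguard is a sensitivity analysis, and none is planned. The Overall objectives hope the result will support a large change in prescribing, so a positive finding should come with a statement of how much selective loss it could withstand.

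**Working it through.** **1. Expected loss.** Inputs: 25 enrolled (Target population) and 25% oversampling (Accrual). If the 25 already includes the oversampling, 25 / 1.25 = 20 completers, and 5 / 25 = 20% are lost. If 25% is instead the loss rate, 25 × 0.75 = 18.75 complete, which is one in four. Both rates are derived; neither is stated.

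**2. The plan's power figure.** Accrual says that a sample "of 25 will have over 99% power to detect differences in outcome", and then "we will have over 90% power to detect significant changes at the 0.01 level for all of the outcomes". These figures cannot be reproduced, because no numerical effect size, SD or within-subject correlation is given. Taking d = 0.5 to 0.8 for moderate to large, a two-sided paired t-test gives:

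| n | Alpha 0.05 | Alpha 0.0125 |
|---|---|---|
| 25 | 67% to 97% | 44% to 89% |
| 20 | 56% to 92% | 33% to 78% |

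The upper end at n = 25 comes close to the plan's figures, and a high within-subject correlation would reach them. What matters here is that power is stated at 25, as if nobody left.

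**3. Bound on the bias.** Let delta be the amount by which the leavers' unseen month-12 change is worse than the model predicts. Then overstatement = share lost × delta. With 20% lost, delta = 0.25 SD gives 0.20 × 0.25 = 0.05 SD, and delta = 1 SD gives 0.20 SD. With 25% lost, the range is about 0.06 to 0.25 SD. No variance assumption is needed, but delta is unknown.

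**4. Simulation.** There were 25 subjects on approximately the planned visit schedule, no true mean change, and 5 lost. All variances are assumptions, because the documents give none.

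- *Setting A:* intercept and residual variance 0.5 each, slope SD 0.05 per month, loss between months 1 and 6, variances treated as known, 1,500 runs. One unit is the baseline SD.
- *Setting B:* slope SD 1 per year, intercept SD 1, residual SD 0.5 or 1, REML fit, 150 trials per scenario. One unit is the SD of the true 12-month change.

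The plan's multiplicity rule is: "Using an alpha of 0.05/4 (Bonferroni correction) to account for multiple outcomes". That is 0.0125. Taken as two-sided, the nominal rate of false improvement is 0.0125 / 2, or about 0.6%; at 0.05 it is 2.5%.

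| What drives loss | Bias (SD) | False improvement at 0.05 | At 0.0125 |
|---|---|---|---|
| A: recorded worsening | about 0 | 2.6% | – |
| A: unrecorded slope, partly to fully | 0.12 to 0.24 | 9% to 18% | 3% to 7% |
| B: recorded scores | about 0 | 2.0% | – |
| B: slope half drives loss, after month 2 | 0.20 to 0.21 | 17% to 19% | see below |
| B: worst five slopes, after month 3 | 0.23 to 0.28 | 31% to 34% | see below |
| B: worst five slopes, after month 1 | 0.32 | 35% to 49% | see below |

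Across the informative-loss scenarios in setting B, the rate at 0.0125 is 9% to 29%. Setting B carries Monte Carlo error of up to about 4 points, and some of its fits gave convergence warnings. Its upper end also requires exactly the five worst true slopes to leave early, so setting A is the steadier guide.

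**5. What a tipping point would show.** If 20 completers gain 0.5 SD on average, the overall mean is zero when (20 × 0.5 + 5 × x) / 25 = 0, so x = -2.0 SD. Statistical significance would be lost before that point.

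**The case against.** The strongest defence is the model itself. Visits are weekly during the taper, and random slopes let each leaver's own recorded trajectory inform the fit. Worsening seen before departure is therefore used, and the simulations bear this out with bias of about zero. A reader might infer that the model projects leavers along the trend of those who stay; the Analysis Plan's specification does not support that. The exposure is limited to loss that depends on response not recorded.

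A reader might also infer that the attrition comparison is between treatment arms that do not exist. The text mentions no arms. Withdrawal could be compared across periods, by sex (to be considered in all analyses) or by taper rate. What stands is that the comparison is unspecified and not tied to pain trajectory or reason for leaving.

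Other points in the plan's favour also stand. The Abstract calls the study an observational pilot. Taper is the centre's standard of care, so leaving the study and stopping the taper are separate events. Visits are paid and aligned with clinic appointments where possible, which helps retention. None of this tests the missing-at-random assumption.

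**Conclusion.** The concern holds in a limited form. Loss is expected in an uncontrolled improvement study, the model relies on an unstated missing-at-random assumption, and no planned step probes it. If recorded scores explain loss, the planned analysis is sound. If unrecorded response partly or fully drives loss of about 5 in 25, the illustrations give bias of about 0.1 to 0.3 SD. False improvement at the plan's 0.0125 is then about 3% to 7% under setting A, against 0.6% nominal, and higher under setting B.

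These sizes rest on assumed variances and an inferred dropout rate. They show what could happen and do not predict this study's error rate. Nor do the documents support saying that a positive result would be survivor selection: a large effect could withstand substantial adverse loss, as the -2.0 SD figure shows. The gap is that the plan, as written, could not show which case applies. It should be closed, at modest cost.

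**What to change.** 1. In the Analysis Plan, state the missing-at-random assumption. Pre-specify one delta-adjusted (pattern-mixture) rerun of the Hypothesis 1 contrast per pain outcome for subjects lost before month 12, reporting the delta at which the conclusion changes.
2. Replace the unspecified comparison with a descriptive summary of leavers against stayers: last recorded pain response, Clinical Opiate Withdrawal Scale score, current morphine-equivalent dose, and reason for leaving. A Cox model with several predictors is not advisable on about five events.
3. State that the planned study assessments continue to be offered to subjects whose taper is paused or stopped. This concerns data collection only and changes nothing in clinical care.

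The cost is some added analysis, recording the reason for leaving, and a few more visits at $25 each. The conclusion may also have to be more cautious.
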